5.3.3. Exploratory endpoints

- 1. Reduction in average headache intensity at 1 month
- 2. Reduction in perceived stress

5.3.4. Safety endpoints

1. The safety of Nerivio

The incidence of adverse events in general and by seriousness, severity and association to the device.

2. Treatment tolerability

The percent of subjects who fail to complete the study because of adverse events.

6. Statistical Considerations

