5.1.3. Withdrawal/discontinuation

Participants may withdraw consent at any time without and do not have to provide an explanation.

Participant may be withdrawn from the study by the PI due to one or more of the following reasons:

- Participant is lost to follow-up
- Refusal of the participant to continue treatment and/or follow-up observations
- · Serious adverse event
- Participants encountering difficulties with the investigational product (IP) (e.g. cannot tolerate the treatment, unable to operate the application)

Revision #: 1.0

Page: 12 of 20

- Significant protocol deviation/violation or noncompliance, either by the patient or the investigator
- Decision made by the investigator that termination is in the patient's best medical interest
- Device malfunction
- Other ethical or clinical considerations upon investigator discretion

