5.2. Procedures

This open label study includes 2 phases and up to 3 visits. All visits will be conducted in the presence of a parent/guardian.

First visit - enrollment: The first visit will include screening, enrollment and training on operating the headache diary within the smartphone application. The screening process will include an eligibility assessment and a urine pregnancy test (if required). Following successful screening, enrollment interview and signing an informed consent by the parent/quardian and an informed assent by the participant. The participants will be trained to use the electronic diary application, installed on their own smartphones. During this visit, participants will complete baseline questionnaires that included information on the headaches (frequency, severity, etc...), typical associated symptoms, use of preventive and abortive medications/treatments, and the effect that their headaches on their daily routine and quality of lifeThe C-SSRS will be administered at the screening visit and a "since last visit" form which will be administered at each subsequent inclinic study visit to assess possible suicidal ideation and behavior. The C-SSRS will be scored by the investigator or Study Coordinator who has C- SSRS certification. The survey will be scored immediately after taken by participant. If reports of suicidal ideation with intent to act (endorse item 4 or 5), reports of actual, aborted, or interrupted suicide attempts, or reports of behavior preparatory for an attempt are identified, the investigator" will refer the subject for further examination.

Phase 1 – run-in phase: After the enrollment visit, participants will undergo a 4-week diary phase aimed to collect baseline NDPH characteristics. Participants will be asked to report in the application each headache attack. These reports will be collected and analyzed.

Second visit – Device training visit: During this visit, participants and their parent/guardian will be trained to use the device, including finding the optimal individual stimulation intensity level (perceptible but not painful).

Participants will be asked to treat their NDPH with the device using the identified optimal intensity. If the research staff recognizes that the participant cannot tolerate the feeling of the electrical stimulation, the participant may be withdrawn from the study.

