6.3. Analysis sets

Intent to treat analysis set (ITT)

The ITT analysis set includes all patients undergoing the treatment phase.

Modified intend to treat analysis set (mITT)

The mITT analysis set includes all patients undergoing the treatment phase and treat at least one (1) treatment within 60 minutes of headache onset. Subjects with no valid post baseline assessment will not be included in the relevant analysis.

Per-protocol analysis set (PP)

The PP analysis set includes all patients from the mITT analysis set without major protocol deviations. Main protocol instructions include:

- has started within 60 minutes of awakening with headache or increased intensity from baseline
 - was administered for 45 minutes
 - includes data on headache intensity at 2 hours post-treatment
 - rescue medication was not used before or within 2 hours post-treatment

Statistical analysis of the analysis sets

The ITT analysis set will serve as the main set for safety assessments.

The mITT analysis set will serve as the primary set for the efficacy assessment.

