6.4.3. Safety analysis

Safety and tolerability will be assessed by review of all safety parameters, including adverse events. Serious adverse events, device-related SAEs, adverse events (by type and overall), device-related AE, adverse device reactions and device malfunction rates will be documented. Treatment tolerability, the number and percent of subjects who fail to complete the study and the number and percent of subjects who fail to complete the study because of adverse events will be presented. Time to withdrawal will also be assessed and presented by Kaplan-Meier curves.

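### The tolerability endpoint counts only non-completion because of adverse events, so intolerance of the stimulation can go uncounted, most clearly at visit 2 training

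*Combined protocol and SAP*

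**What the plan says.** - **Endpoint.** Section 5.3.4 (and the synopsis) defines treatment tolerability as "The percent of subjects who fail to complete the study because of adverse events". Section 6.4.3 repeats this: "the number and percent of subjects who fail to complete the study because of adverse events will be presented". It also plans all-cause non-completion and Kaplan-Meier curves of time to withdrawal.
- **Grounds for withdrawal.** Section 5.1.3 opens with "Participant may be withdrawn from the study by the PI due to one or more of the following reasons". One item is "Serious adverse event". A different item is "Participants encountering difficulties with the investigational product (IP) (e.g. cannot tolerate the treatment, unable to operate the application". No item names a non-serious adverse event.
- **Visit 2.** Section 5.2, on the device training visit at which the individual stimulation intensity is found, says: "If the research staff recognizes that the participant cannot tolerate the feeling of the electrical stimulation, the participant may be withdrawn from the study". It does not say whether this is recorded as an adverse event.
- **Population.** Section 6.3: "The ITT analysis set includes all patients undergoing the treatment phase". This is the main set for safety, and section 6.4.1 likewise limits safety analyses to participants who underwent the treatment phase.

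**The concern.** The plan names inability to tolerate the stimulation twice as a ground for leaving, then defines tolerability without mentioning it. No sentence says whether such a withdrawal counts as one because of an adverse event, so the answer is left to how each case is recorded.

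For a device that works by felt stimulation of the upper arm, stopping because the stimulation cannot be borne is a central form of tolerability failure. The study has a single arm, so no control rate would reveal an undercount. Safety is half of the stated objective. A low figure for this endpoint could be read as good tolerability when it partly reflects where the withdrawals were filed, or that they happened before the analysis set begins.

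**Working it through.** The documents give no expected tolerability rate or dropout rate, so there is no plan figure to reproduce. The check has two parts.

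**1. Does the text bring intolerance into the numerator?**

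- Section 10 defines an adverse event as a medical change that is both unfavourable and unintended. Section 10.3 lists arm pain, tingling, numbness, muscle spasms and warmth among the anticipated device-related events, and section 10.2 has all adverse events recorded. Intolerance that presents as one of these can be counted.
- Section 5.2 has the stimulation set so that it is felt but does not hurt. A participant who cannot bear an intended sensation need not have an unintended medical change. That case can be withdrawn under 5.1.3 or 5.2 with no adverse event recorded.
- In 5.2 the procedures place visit 2 after Phase 1 and before Phase 2. The synopsis describes receipt of the device under Phase II. Whether a participant withdrawn at visit 2 has undergone the treatment phase is therefore not settled. If not, that participant is in neither numerator nor denominator, and also outside the all-cause figure if 6.4.1 is applied to it.

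**2. How far could the figure move?** All counts below are assumed. Let A be withdrawals attributed to an adverse event, T treatment-phase intolerance withdrawals not so attributed, V visit 2 intolerance withdrawals, and N participants entering the treatment phase.

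- As written: A/N
- Intolerance counted, same denominator: (A + T)/N
- Intolerance counted among all stimulated: (A + T + V)/(N + V)

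| A | T | V | N | As written | Same denominator | All stimulated |
|---|---|---|---|---|---|---|
| 1 | 5 | 5 | 95 | 1/95 = 1.1% | 6/95 = 6.3% | 11/100 = 11% |
| 1 | 2 | 2 | 98 | 1/98 = 1.0% | 3/98 = 3.1% | 5/100 = 5% |

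In the first row the numerator change adds 5/95 = 5.3 percentage points, and the visit 2 participants add 11.0 − 6.3 = 4.7. The two effects are separate and about equal.

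For precision, take 100 stimulated participants with A = 2 and exact two-sided 95% intervals:

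| Intolerance withdrawals not attributed to an adverse event | As written, if all occur in the treatment phase | As written, if all occur at visit 2 and fall outside the set | Intolerance counted, all stimulated |
|---|---|---|---|
| 0 | 2.0% (0.2 to 7.0) | 2.0% (0.2 to 7.0) | 2.0% (0.2 to 7.0) |
| 5 | 2.0% (0.2 to 7.0) | 2/95 = 2.1% (0.3 to 7.4) | 7.0% (2.9 to 13.9) |
| 10 | 2.0% (0.2 to 7.0) | 2/90 = 2.2% (0.3 to 7.8) | 12.0% (6.4 to 20.0) |

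The endpoint as written barely responds to the number of intolerant participants.

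**Limiting case.** If all 5 treatment-phase cases in the first row of the first table are also attributed to an adverse event, the endpoint as written is 6/95 = 6.3% and the treatment-phase undercount is zero. Only the visit 2 question remains: 6.3% against 11%.

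**The case against.** The strongest reply is that the list in 5.1.3 gives grounds for withdrawal, not exclusive reason codes. It allows more than one reason at once, so one participant can be both intolerant of the device and a non-completer because of an adverse event. With the broad definition in section 10 and the anticipated events in 10.3, much intolerance would be recorded as adverse events. Section 6.4.3 also reports all-cause non-completion, so treatment-phase cases would not vanish from the report. Whether people who fail initial training belong in a tolerability rate is a design choice.

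Most of this stands, and it rules out two stronger readings. A reader might infer that the endpoint necessarily misses intolerance; the documents do not support that, because the grounds can overlap and many cases qualify as adverse events. A reader might also infer, from the single adverse-event item in 5.1.3, that the endpoint amounts to the rate of withdrawal for serious events. It does not: 5.3.4 says adverse events without restriction, and a non-serious event can lead to withdrawal under the investigator's medical judgement or by the participant's own decision.

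The reply does not close the gap. Nothing requires an intolerance withdrawal to be attributed to an adverse event, and an intended sensation need not be one. The all-cause total mixes intolerance with loss to follow-up, application problems and device malfunction. No table by reason is planned, and 5.1.3 puts intolerance and inability to operate the application in one item. None of the reply reaches participants withdrawn at visit 2.

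**Conclusion.** The point holds as a gap in the definition: the endpoint can miss intolerance that is not attributed to an adverse event, and it may exclude altogether those withdrawn for intolerance at visit 2 after being stimulated. The size cannot be known from the documents. During the treatment phase it runs from zero, if every case is attributed to an adverse event, to the full count of intolerance withdrawals, if none is. At visit 2 it depends on whether that visit counts as part of the treatment phase, which is not stated.

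The 6.3% and 11% figures rest on invented counts and on no intolerance case being attributed to an adverse event. They show sensitivity and are not estimates. The contrast of 1.1% with 11% should not be read as the effect of the numerator alone, because it also changes the denominator. The change is worth making because it costs little and the endpoint would otherwise depend on recording habits.

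**What to change.** 1. In 5.3.4, the synopsis and 6.4.3, define tolerability failure as non-completion because of any adverse event, serious or not, or because the participant could not tolerate the stimulation.
2. For this endpoint, use as denominator everyone who received any stimulation, including at visit 2 training. Show the rate among treatment-phase participants beside it, so that the two effects can be told apart.
3. In 6.4.3, tabulate non-completion by reason, with intolerance of the stimulation separate from inability to operate the application.

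The cost is wording, one additional recorded reason, and a record of who received stimulation at visit 2. The reported tolerability figure may be less favourable. The criteria for withdrawing participants do not change.

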6.1. Study design and aim

The study is designed as a prospective, open label study. This study aims to evaluate the safety and efficacy of Nerivio[™] for the acute treatment of NDPH in adolescents (ages 12-17 years).

6.2. Sample size

100 participants

Revision #: 1.0

Page: 16 of 20

6.3. Analysis sets

Intent to treat analysis set (ITT)

The ITT analysis set includes all patients undergoing the treatment phase.

Modified intend to treat analysis set (mITT)

The mITT analysis set includes all patients undergoing the treatment phase and treat at least one (1) treatment within 60 minutes of headache onset. Subjects with no valid post baseline assessment will not be included in the relevant analysis.

Per-protocol analysis set (PP)

The PP analysis set includes all patients from the mITT analysis set without major protocol deviations. Main protocol instructions include:

- has started within 60 minutes of awakening with headache or increased intensity from baseline
 - was administered for 45 minutes
 - includes data on headache intensity at 2 hours post-treatment
 - rescue medication was not used before or within 2 hours post-treatment

Statistical analysis of the analysis sets

The ITT analysis set will serve as the main set for safety assessments.

The mITT analysis set will serve as the primary set for the efficacy assessment.

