5.1. Participants

This study will be conducted on up to 100 eligible participants.

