During the training, participants will also be informed on the key elements which are critical for the successful conduct of the study:

Revision #: 1.0 Page: 13 of 20

- Treatments of headache with Nerivio[™] should be performed within 60 minutes of awakening with a headache or upon increasing headache severity and always within one hour of symptoms onset. Treatments of mild headaches are accepted.
- Avoid taking rescue medications within two hours post-treatment (2 hours from start of treatment), if possible.

Revision #: 1.0

Page: 14 of 20

• The treatment should be performed for 45 minutes.

In addition, participants will complete study questionnaires, as required.

Phase 2 – Treatment phase: Participants will be instructed to use the device within 60 minutes of awakening with a headache or upon increasing headache severity during a period of 4 week. Participants will be instructed to use the device with the intensity level identified during the device training visit (with a range of ±5 units) and make sure the stimulation is perceptible but not painful. Participants will be instructed to avoid taking rescue medications within 2 hours post-treatment. If medications are used, participants will be instructed to record in the app when and which medication was taken. The participants will use the app to record pain intensity levels (none, mild, moderate, or severe) at baseline and 2 hours post-treatment, and to record the presence/absence of associated symptoms (nausea, photophobia, phonophobia) at baseline and 2 hours post-treatment.

Participants who do not achieve satisfactory relief at 2 hours post-treatment may treat again with the Nerivio[™] device or may treat with usual care at that time or any time thereafter if the headache does not resolve.

Third (final) visit – End of study: Participants will return to the clinic following the end of the 4-week treatment phase, at which time they will return the device and complete the required questionnaires

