6.4. Statistical analysis

6.4.1. General considerations

Statistical analyses will be performed using SAS® v9.4 or higher (SAS Institute, Cary NC, USA).

Baseline demographic and other baseline characteristics, together with safety analyses will be performed on all participants who underwent the treatment phase. Baseline values are defined as the last valid value prior to treatment.

Where confidence limits are appropriate, a two-sided 95% confidence interval will be constructed.

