6.4.4. Efficacy analysis

The efficacy endpoints will be assessed on evaluable treatments of qualifying attacks. The first use of the device is considered a training treatment and will not be included in the efficacy analyses. The first treatment of a qualifying attack after the training treatment is considered a test treatment and will be used for all efficacy assessments. If this treatment is not evaluable (i.e., no pain data at 2 hours post-treatment), a subsequent treatment of a qualifying attack with evaluable data will be considered the test treatment.

Use of rescue medication before the 2-hours assessment will be considered a treatment failure for the 2-hours endpoints, and before the 24 hours assessment for the sustained 24-hours endpoints. The percentage of participants achieving each of the efficacy outcomes will be presented in a tabular form along with two-sided 95% exact confidence intervals.

For the associated symptoms outcomes, the observed response proportions and corresponding 95% exact confidence intervals for each associated symptom will be provided. All patients with baseline and 2 hours values will be included in the analyses. A response in each associated symptom (nausea, vomiting, photophobia, phonophobia) is defined as change from presence of a specific associated symptom at baseline to absence of the same associated symptom at 2 hours post-treatment.

In addition, logistic regression models will be used to assess the efficacy. Baseline value and site will serve as covariates.

The first secondary endpoint (pain relief at 2 hours) may also be evaluated in attacks with aura and attacks without aura separately.

7. Data management

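### Participants who stop before an evaluable test treatment leave the primary response rate instead of counting as failures, and those who stop the device are not asked to attend the final visit

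*Combined protocol and SAP*

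**What the plan says.** **Efficacy set.** Section 6.3 states: "The mITT analysis set will serve as the primary set for the efficacy assessment". Entry to the mITT set requires at least one treatment started within 60 minutes of onset, and the section continues: "Subjects with no valid post baseline assessment will not be included in the relevant analysis". The synopsis ties mITT entry to the test treatment itself. ITT is named as the main set for safety, and the per-protocol set is a subset of mITT.

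**What is scored.** Section 6.4.4 states: "The first use of the device is considered a training treatment and will not be included in the efficacy analyses". The next treated qualifying attack is the test treatment. If it has no 2-hour pain value, a later qualifying attack with data takes its place. Rescue medication before the 2-hour assessment is scored as failure. Stopping the device has no corresponding rule.

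**Leaving the study.** Section 5.1.3 opens its list with "Participant may be withdrawn from the study by the PI due to one or more of the following reasons". The grounds include inability to tolerate treatment, device malfunction, a serious adverse event, and refusal of treatment or follow-up (one shared item). Section 5.2 adds possible withdrawal for intolerance at the training visit.

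**Last visit.** Section 5.2 says of the third visit: "Participants will return to the clinic following the end of the 4-week treatment phase". Questionnaires are completed then, and the C-SSRS is given at in-clinic visits. No early-termination visit, follow-up after stopping the device, or missing-data method is described.

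**The concern.** In an open-label, single-arm study the response proportion and its confidence interval are the main efficacy evidence, and no control arm carries the same selection. A participant who tries the device once, finds it unpleasant or of no use, and stops has no test treatment. Such stopping is plausibly related to outcome. Leaving these participants out, with no failure rule, would tend to raise the reported rate above the rate among everyone given the device.

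The 1-month questionnaire endpoints raise a related issue. If stopping the device leads to leaving the study, the PedsMIDAS change becomes a result for those who stayed, and the final C-SSRS may be missing for those who left because of a problem with the device. Values not collected at that visit cannot be recovered afterwards.

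**Working it through.** **The plan's own figure.** Section 5.1 says "This study will be conducted on up to 100 eligible participants" and section 6.2 says only "100 participants". No response rate, reference rate, power, precision target or dropout allowance is given, so the 100 cannot be reproduced. The point concerns denominators and does not depend on it.

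**Step 1: who is in the primary denominator.** Reading 6.3 and 6.4.4 together:

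| Participant | Scored test treatment? | Primary proportion |
|---|---|---|
| Stops after only the first (training) use | No | Left out |
| Continues, but never has 2-hour data for a qualifying attack | No | Left out |
| Takes rescue medication before 2 hours in the test treatment | Yes | Failure |
| Stops after one evaluable test treatment | Yes | Counted as observed |

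The first row holds under either mITT wording. Under the synopsis this participant is outside the set; under 6.3 the participant may be inside it but has no outcome for the analysis. The replacement rule in 6.4.4 helps only those who go on to treat another attack. The logistic regression in 6.4.4 cannot use a participant without an outcome.

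**Step 2: size, by illustration.** Let N be the number given the device, k the number with no evaluable test treatment, and p the response rate among the N − k evaluable.

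- Rate as planned = p.
- Rate with the k counted as failures = p × (N − k)/N.
- Gap = p × k/N.

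Inputs: N = 100 is the planned maximum. The interval is two-sided 95% (6.4.1: "a two-sided 95% confidence interval will be constructed") and exact (6.4.4), computed as Clopper-Pearson. The values p = 60% and k = 5 to 30 are assumptions; the documents give neither.

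| k | As planned (95% CI) | Failures imputed (95% CI) | Gap |
|---|---|---|---|
| 0 | 60/100 = 60.0% (49.7–69.7) | same | 0 |
| 5 | 57/95 = 60.0% (49.4–69.9) | 57/100 = 57.0% (46.7–66.9) | 3 points |
| 10 | 54/90 = 60.0% (49.1–70.2) | 54/100 = 54.0% (43.7–64.0) | 6 points |
| 20 | 48/80 = 60.0% (48.4–70.8) | 48/100 = 48.0% (37.9–58.2) | 12 points |
| 30 | 42/70 = 60.0% (47.6–71.5) | 42/100 = 42.0% (32.2–52.3) | 18 points |

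For p from 40% to 70%, the gap is 0.40 × 5 = 2 to 0.70 × 5 = 3.5 points at k = 5, and 0.40 × 30 = 12 to 0.70 × 30 = 21 points at k = 30. For scale, the half-width of a 95% interval at 50% with N = 100 is 1.96 × √(0.25/100) = 9.8 points. A loss of 20 at p = 60% therefore shifts the rate by more than the sampling error that the interval shows.

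**Step 3: timing of stopping.** Suppose 20 of 100 stop early and none attends the third visit. The denominator for the third-visit questionnaires is 80 whatever the timing. The primary denominator depends on how many of the 20 stop before an evaluable test treatment:

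| Stop before test treatment | Primary denominator | Failure-imputed rate at p = 60% |
|---|---|---|
| 0 | 100 | 60% (no gap) |
| 5 | 95 | 57% |
| 10 | 90 | 54% |
| 20 | 80 | 48% |

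**The case against.** Several stronger readings are tempting, and the documents do not support them.

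- A reader might infer that the primary rate describes only participants who kept using the device. It does not: one evaluable treatment after training is enough, and stopping later changes nothing in that rate.
- A reader might infer that an early stopper is missing from every efficacy result. Section 6.3 excludes only from the relevant analysis, so someone with no test treatment who attends the third visit could still supply PedsMIDAS and HIT-6.
- A reader might infer that stopping the device means leaving the study with no final visit. Withdrawal by the investigator is discretionary in 5.1.3 and 5.2, and nothing bars a stopper from returning. What stands is that nothing asks for it either.
- A reader might infer that ITT is barred from efficacy. Section 6.3 calls it the main safety set, which is not exclusive. The accurate statement is that no ITT efficacy analysis is specified.
- A reader might infer that withdrawals, or the course of adverse events, go unreported. Section 6.4.3 presents withdrawals overall and for adverse events, with Kaplan-Meier curves. Sections 10.1 and 10.2 require all adverse events to be recorded, with start and stop dates.

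Three further objections are fair. The rescue rule already scores some lack of benefit as failure. Pain intensity is recorded in the app, so the headache-intensity endpoint may not depend on the third visit, and 5.2 does not list which questionnaires are completed there. The plan has no performance goal or test, so a shifted rate changes no stated decision.

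These points narrow the concern without removing it. Reporting withdrawals shows attrition but leaves the efficacy denominator as it is, and a descriptive percentage is the study's main efficacy result.

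**Conclusion.** The point holds in a limited form. Participants who enter the treatment phase but have no evaluable test treatment are left out of the primary proportion, with no failure rule and no specified analysis that counts them. Separately, the plan does not seek third-visit data from those who stop the device, so PedsMIDAS and the other third-visit questionnaire endpoints may rest on those who stayed.

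The likely direction for the primary rate is upward, on the assumption that stopping before a scored treatment goes with intolerance or lack of benefit. The size cannot be known from the documents. It is 3 to 12 points for 5 to 20 such participants in 100 at an assumed 60% response, and zero if all stoppers leave after an evaluable test treatment. The change is worth making because it is cheap; the third-visit part must be in place while participants can still be followed.

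**What to change.** 1. **Sections 6.3 and 6.4.4.** Add a prespecified analysis of 2-hour pain relief on all participants given the device at the second visit, including any withdrawn at or after device training, with no evaluable test treatment counted as non-response. Report it beside the mITT result, with counts and reasons for non-evaluability. Define the denominator in these words and not simply as ITT, because someone withdrawn at training may not count as having undergone the treatment phase.
2. **Section 5.1.3.** Distinguish stopping device use from withdrawing from follow-up. Ask those who stop the device but do not withdraw consent to complete the already planned third-visit questionnaires, C-SSRS and adverse-event review, and include their values in the 1-month endpoints. The grounds for stopping stay unchanged.

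The cost is one extra table, a short amendment, and possibly a lower reported response rate. No new visit is needed.

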5.3. Study endpoints

5.3.1. Primary endpoints

1. Pain relief at 2 hours post-treatment:

The proportion of participants achieving pain relief at 2 hours post-treatment in the test treatment, with no use of rescue/abortive medication (Pain relief defined as a reduction in pain scale from severe to moderate, mild, or none)from moderate or severe to mild or none.

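### For the 2-hour responder endpoints, the per-protocol rescue condition removes participants whom the main analysis counts as failures, so that condition on its own biases the per-protocol rate upward

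*Combined protocol and SAP*

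**What the plan says.** Section 6.3 defines three analysis sets. On the third it says: "The PP analysis set includes all patients from the mITT analysis set without major protocol deviations". It then lists what it calls the main instructions of the protocol: start within 60 minutes, a 45-minute session, pain data at 2 hours, and "rescue medication was not used before or within 2 hours post-treatment".

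The primary endpoint in 5.3.1 is the proportion of participants with "pain relief at 2 hours post-treatment in the test treatment, with no use of rescue/abortive medication". Section 6.4.4 applies the same principle in the analysis: "Use of rescue medication before the 2-hours assessment will be considered a treatment failure for the 2-hours endpoints".

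On the roles of the sets, 6.3 states: "The mITT analysis set will serve as the primary set for the efficacy assessment". The intent-to-treat set is for safety. No analysis is assigned to PP, the synopsis does not list it, and 6.4.4 does not mention it.

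Rescue use is foreseen. The training points in 5.2 read "Avoid taking rescue medications within two hours post-treatment (2 hours from start of treatment), if possible", and participants who do take medication are asked to record it in the app.

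**The concern.** Rescue taken after the session has started is part of the outcome. A participant who takes it before the 2-hour assessment cannot be a responder under 5.3.1 and 6.4.4. A PP condition that removes such participants selects on the outcome: it takes failures out of the denominator and leaves the numerator unchanged.

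The trial has a single arm, and its results are to be read from absolute proportions with "two-sided 95% exact confidence intervals". There is no control group in which the same exclusion could partly cancel. If a PP rate is reported next to the mITT rate, a higher PP figure could be taken for a better effect under correct use, and a similar one for robustness, when part of either comes from the definition of the set.

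**Working it through.** **Inputs from the documents.** Rescue before 2 hours is a failure (5.3.1, 6.4.4). Rescue before or within 2 hours breaches a PP condition (6.3). Intervals are exact, two-sided, 95% (6.4.4). Section 6.2 gives "100 participants" with no supporting assumptions. There is no planned response rate, rescue rate or PP estimate to reproduce.

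**Assumptions.** The denominator of 100 is illustrative, since the plan says up to 100 and participants must first pass a run-in. The 45% response and the numbers of rescue users are assumed.

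**Formula.** Let N be the evaluable mITT participants, R the responders and M the participants who used rescue before 2 hours, all of them failures by rule.

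- mITT rate = R/N
- PP rate from the rescue condition alone = R/(N − M)
- Ratio of PP to mITT = N/(N − M) = 1/(1 − M/N), which is above 1 whenever M > 0; the PP rate is then higher provided R > 0.

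**Numbers with N = 100, R = 45 (mITT 45.0%).**

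| Rescue users M | PP rate from this condition | Shift in points |
|---|---|---|
| 5 | 45/95 = 47.4% | 2.4 |
| 10 | 45/90 = 50.0% | 5.0 |
| 20 | 45/80 = 56.3% | 11.3 |
| 30 | 45/70 = 64.3% | 19.3 |

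With M = 20 the exact 95% interval moves from 35.0–55.3% (45/100) to 44.7–67.3% (45/80).

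**Range.** Over 5 to 30 rescue users and an mITT response of 30% to 60%, the smallest shift is 30/95 − 30/100 = 31.6% − 30.0% = 1.6 points. The largest is 60/70 − 60/100 = 85.7% − 60.0% = 25.7 points.

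**Effect of the other PP conditions.** Take N = 100, R = 50, M = 5, and 10 further participants dropped for timing or duration.

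- If 5 of those 10 were responders, PP = (50 − 5)/(100 − 10 − 5) = 45/85 = 52.9%, against 50% in mITT.
- If all 10 were responders, PP = (50 − 10)/85 = 40/85 = 47.1%, below the mITT rate. Keeping the rescue users in as failures would give 40/90 = 44.4%.

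The net PP rate can therefore fall below mITT, but the rescue condition pushes it up in both cases.

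**Starting point of the two rules.** The failure rule in 6.4.4 covers any rescue before the 2-hour assessment and gives no earliest time. Read literally, medication taken before the session also makes a participant an mITT failure. Deleting only the within-2-hours part of the PP bullet would leave its remaining word for earlier use without a reference point, and PP would still remove participants whom 6.4.4 counts as failures.

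**The case against.** The strongest reply is that no planned estimate changes. mITT is the primary efficacy set, it already counts rescue as failure, and PP has no assigned analysis. Misreading of a PP result is a possibility, not something the plan sets out to do. This stands, and it limits the importance of the point.

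A reader might infer that any PP rate must exceed the mITT rate. The documents do not support that. The 60-minute and 45-minute conditions can lower the rate, as the 47.1% example shows. Nor does the argument reach PedsMIDAS or the exploratory measures, for which rescue is not defined as failure.

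It can also be said that exclusion is inferred: 6.3 lists instructions and does not call each breach a major deviation. That is true. Exclusion remains the natural reading, because the list has no other function in the definition of the set.

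Finally, participants are told to avoid rescue, so a set of adherent participants may fairly answer a different question and be expected to be selective. This holds for conditions on how the device was used. It is weaker for rescue after the start, because avoidance is asked for only where possible and the event itself decides the endpoint. Labelling PP as supportive and reporting exclusions by reason would help the reader but would not remove the bias.

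The PP bullets describe a treatment while the set consists of patients. Section 6.4.4 largely answers this by using the test treatment for all efficacy assessments, but 6.3 does not say so.

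**Conclusion.** The point holds for the 2-hour responder endpoints and for the rescue condition taken alone. Given at least one rescue user and one responder, that condition multiplies the response rate by 1/(1 − M/N). The direction follows from the definitions; the size depends on rates that the documents do not give. At an assumed 45% response in 100 participants, the shift runs from 2.4 points with 5 rescue users to 19.3 points with 30.

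A reader might go further and conclude that the trial's primary efficacy result is biased by this condition. It is not: the mITT analysis keeps rescue users as failures. The change is worth making because mITT's status as the primary set implies a supporting role for PP, and an estimate that conditions on its own outcome cannot fill that role.

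**What to change.** Change analysis wording only; no participant instruction is touched.

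1. In 6.3, replace the rescue bullet. Rescue taken between the start of the test treatment and the 2-hour assessment is not a reason for exclusion from PP and counts as failure, as in mITT.
2. Limit any rescue-related PP exclusion to medication taken before the start of the test treatment, and give the failure rule in 6.4.4 the same starting point so that the two sections agree.
3. State that the PP conditions apply to the test treatment.
4. Label PP as a supportive sensitivity analysis of the primary endpoint, and report the number excluded by reason.

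The cost is a short text amendment. The PP estimate becomes less favourable: in the example with 20 rescue users it returns from 56.3% to 45.0% as far as this condition is concerned.
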